7.6 Protocol non-compliance/deviation

Any protocol deviations and instances of non-compliance will be summarised.

8 Health Economics Analysis plan

8.1 Aims

Conducting a prospective economic evaluation to develop and refine methods for a subsequent definitive trial

8.2 Analysis

8.2.1 Costs

The use of health and social care services will be converted into costs by combining data on the use of each specific service with a unit cost for that service. For example, the cost of the GP appointments will depend upon how many appointments took place and the price per unit of that appointment. Costs will be estimated based on the data provided from "within the study" CRFs supplemented by information from the literature, data drawn routine UK health service databases, and social care services. At the end of the study, costs will be estimated for each participant in each treatment group. The specific resource use categories included in the cost-effectiveness analysis will be:

- (1) Cost of iSupportPD. This will include the cost of hosting, running, and maintaining the website.
- (2) Costs of resource use at follow-up. These will also include costs of resource utilization within primary, community, secondary and personal social service settings.

Costs, where relevant, will include the variable cost and a portion of the fixed cost related to the lifetime of the resource and how often it can be used(5). For each participant use of services will be multiplied by appropriate unit costs to calculate total cost for each participant. Unit costs for healthcare services will be obtained from standard sources such as NHS reference Healthcare Resource Group (HRG) tariff(6) or Unit costs of Health and Social Care(7) for contacts with primary care, community and social care. Costs will be estimated using 2021/22

prices. The most recent unit costs will be used where possible, with unit costs prior to 2021/22 being inflated using the relevant inflation index(7).

8.2.2 Health-related quality of life

Quality of life will be measured using EQ-5D-5L. Utilities values will be mapped to the EQ-5D-3L UK specific value set(3). Utility scores will be combined with length of life over the study follow-up to calculate QALYs, using an area under the curve approach and assuming linear extrapolation between time points(8). Specifically, the area under the curve equates to the total QALY value where QALYs are calculated by multiplying duration of time in a health state by the utility score (equation 1).

Total QALYs =
$$\left(\frac{u_1+u_2}{2} * p_1\right) + \left(\frac{u_2+u_3}{2} * p_2\right) + \cdots$$
 (1)

Where u is the EQ-5D-5L utility value for each time period (1,2,3...) and p is the difference between the two time periods. In addition, the social care-related quality of life (SCRQoL) will be measures using the Adult Social Care Outcomes Toolkit (ASCOT) for carers.

8.3 Cost-effectiveness analysis

Both a cost effectiveness and cost utility analysis will be conducted from a personal health and social care services and a societal perspective. The cost utility analysis will be based on EQ-5D quality adjusted life years (QALYs) and both will estimate costs

Our analysis will take both an NHS and personal social services (PSS) and a societal perspective as we expect costs and savings will also accrue to family members. Incremental cost effectiveness ratios (ICER) and cost effectiveness acceptability curves (CEACs) will be produced comparing provision of iSupport-PD vs usual care. The economic analyses will follow CHEERS guidelines(9).

All health economic outcomes (resource use, costs, QALYs) will be described with the appropriate descriptive statistics. The continuous and count outcomes will be expressed as mean ± standard deviation or medians and inter-quartile range where appropriate and dichotomous and categorical outcomes will be presented as absolute numbers and percentages. Analysis of costs and outcomes (QALYs. SQALYs) will estimate the mean differences (with a bootstrapped 95% confidence interval) between the intervention and control groups(10). For each study participant a total cost and a QALY score will be estimated.

Total costs and total QALYs for each patient will be estimated using a pattern mixed linear regression model to estimate total costs and total QALYs. Each model will include the following predictors:

- Allocation: Intervention or Control
- Time
- Allocation x time interaction term
- Baseline utility score
- Correlation of observations within participants over time, modelled by a covariance structure random effect.

The joint estimates of costs and effects from these models will be combined in an incremental analysis between intervention and control groups and will be presented as the point estimate of

mean incremental cost-effectiveness ratio (ICER) for intervention versus control. The ICER will be calculated as difference in costs divided by difference in effects (QALYs) between two interventions. Measures of variance for the joint incremental costs and effects will be obtained using non-parametric bootstrapping and presented graphically using the cost-effectiveness plane and cost-effectiveness acceptability curves.

To help identify the optimal approach, the net monetary benefit (NMB) framework will be used, where the NMB for a given strategy is equal to the accrued QALYs multiplied by the ceiling ratio (CR) of willingness to pay (WTP) per QALY, minus the strategy costs. Thus,

NMB = (QALYs * CR) - Costs

Although there are currently no agreed cost-effectiveness thresholds regarding social care interventions, values of £20,000 and £30,000 per QALY will be presented in the main results, alongside a cost-effectiveness acceptability curve presenting cost-effectiveness of values between £0 and £100,000 per QALY.

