8.4 Missing data

Missing data will be quantified per data item (%). Ignoring small amounts of missing data (e.g., <5% of the observations) is acceptable if the amount and pattern of missing data are similar across treatment groups and a reasonable case can be made that doing so is unlikely to bias treatment group comparisons. As total cost is calculated as a sum of numerous components, if one component is missing then the total cost will be missing. Such complete case analysis may introduce bias if those with complete data differ from those with partial data. The method to handle missing data will be grounded in a plausible assumption regarding the missing data mechanism. Rubin's framework will be utilised for classifying missing data in order to define assumptions and choose an appropriate analysis method for the base case. (11) If Missing At Random (MAR) is suggested, we will incorporate multiple imputation with chained equations (MICE) to deal with missing cost and utility data. Data are missing at random (MAR) if the probability that data are missing is independent of unobserved values, given the observed data (including previous outcome measurements). Therefore, any systematic differences between the observed and unobserved values can be explained by differences in observed variables. Although the linear mixed effect model proposed for the cost-effectiveness analysis can also be used to deal with missing data under a MAR assumption, it has several limitations compared to multiple imputation(12). Firstly, as the linear mixed model is pre-specified, it is inflexible and cannot adjust for potential observed variables which impact missing data. This contrasts with multiple imputation in which missing data is imputed using a separate model, which can be adjusted for observed variables driving missing data. Secondly, multiple imputation allows further flexibility and potential sensitivity analysis to be conducted around the imputed missing data variables. Furthermore, combination of multiple imputation around a linear mixed model analysis has been identified as more efficient in trial-based cost-effectiveness analysis compared to just using linear mixed effects models alone(13).

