A second consideration relates to the nature of costs, which as discussed previously is built up from numerous components. A balance needs to be struck between maintaining the data structure (hence imputing at more disaggregated level) and achieving a stable imputation model (which becomes more difficult as more variables with missing data are added(14). The choice of approach should be informed by the structure of the data, the pattern of missing data and by testing a variety of approaches. For costs, imputing at the total cost level is likely to be appropriate when the different types of resource use that make up the cost have the same pattern of missing data. We anticipate that analysis and imputation of costs will be conducted

at the aggregate level as this has been reported to be appropriate (12). We anticipate that missing EQ-5D data will not typically be domain specific and will be either reported or not in its entirety. Therefore, we anticipate, missing QALY data to be analysed and imputed at the aggregate score level (15).

Following analysis of the data sensitivity analysis will be conducted regarding methods for imputation. In particular, pattern mixture modelling will be used to conduct sensitivity analysis to allow potential plausible changes to missing data in order to investigate possible MNAR scenarios(12).

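### The base-case cost-effectiveness model in SAP 8.3 pairs one-per-participant totals with repeated-measures terms and never states how the incremental cost and QALY are obtained

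*SAP*

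**What the plan says.** SAP 8.2.1 multiplies each participant's service use by unit costs to reach one total cost. SAP 8.2.2 (equation 1) turns the visit utilities into one total QALY by the area under the curve. SAP 8.3 repeats this level: "For each study participant a total cost and a QALY score will be estimated". It then gives the base-case model: "Total costs and total QALYs for each patient will be estimated using a pattern mixed linear regression model".

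The predictors listed for each model are allocation, time, "Allocation x time interaction term", "Baseline utility score" and "Correlation of observations within participants over time, modelled by a covariance structure random effect". The cost and QALY estimates from these models are then combined into the ICER, with bootstrapping for the cost-effectiveness plane and acceptability curves. No contrast or weighting is given for that step.

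SAP 8.4 describes the model differently: "the linear mixed effect model proposed for the cost-effectiveness analysis can also be used to deal with missing data under a MAR assumption". It reserves a similar-sounding term for departures from missing at random: "pattern mixture modelling will be used to conduct sensitivity analysis".

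SAP section 4 says that allocation is minimised on carer age, relationship to the person with Parkinson's, and gender. None of these is among the listed predictors.

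**The concern.** The outcome and the predictors belong to two different models. A 12-month total has one row per participant, so time does not vary and there are no repeated observations to correlate. Time, the interaction and the random effect make sense only if the rows are visit utilities and period costs, and the SAP nowhere says that they are. It also leaves open whether time is categorical or continuous.

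The remark in 8.4 about handling missing data under MAR points to repeated rows, because a mixed model gains from partly observed participants only if they contribute some visits. The same section expects costs and QALYs to be analysed and imputed at aggregate level, which leaves the row level unclear again.

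The ICER, net monetary benefit and acceptability curves depend on the two increments from this model. Two analysts following the text could fit different models or take different quantities from the same fit. The stated economic aim (SAP 8.1) is to refine methods for a definitive trial, so the specification is itself something the study delivers.

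**Working it through.** The plan states no figure on this point, so there is nothing to reproduce. The check is whether each reading of the model is identified and what it yields.

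**Inputs from the SAP.** Visits at 0, 3, 6 and 12 months (5.3), that is 0, 0.25, 0.5 and 1 year; equation 1 (8.2.2); the predictor list and the ICER definition (8.3). All effect sizes, costs and sample sizes below are illustrative assumptions.

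**Reading 1: one total per participant.**
- The fixed-effect columns are intercept, allocation A, time T, A×T and baseline utility.
- T takes the same value c for everyone, so T = c × intercept and A×T = c × A. Only intercept, A and baseline utility are independent: 5 columns, rank 3. A numerical check with 60 simulated participants gave the same.
- With one observation each, the variance of the outcome is τ² + σ² (random effect plus residual), and only the sum enters the likelihood. With the sum fixed at 0.01 and τ² set to 0, 0.002, 0.005 or 0.009, the log-likelihood was 62.747 each time.
- Fitting the full mixed model stopped with a singular-matrix error. With the redundant terms removed, the regression on allocation and baseline utility fits, and its allocation coefficient is the increment.

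**Reading 2: one row per participant and visit, categorical time.**
- Weights from equation 1: T0 = 0.25/2 = 0.125; T1 = 0.125 + 0.125 = 0.25; T2 = 0.125 + 0.25 = 0.375; T3 = 0.5/2 = 0.25. They sum to 1.
- With baseline adjustment the arms do not differ at T0, so ΔQALY = 0.25·d(3m) + 0.375·d(6m) + 0.25·d(12m).
- ΔCost = the sum of the three period differences.
- With T1 as reference, the allocation coefficient is β = d(3m), and the interactions are γ6 = d(6m) − d(3m) and γ12 = d(12m) − d(3m). Hence ΔQALY = 0.875β + 0.375γ6 + 0.25γ12 and ΔCost = 3β + γ6 + γ12. Neither is a single coefficient.
- A simulated fit (20,000 participants, true differences 0.02, 0.04 and 0.06) ran without trouble. The weighted contrast was 0.0345 against a true 0.035, while the allocation coefficient was 0.019.

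**What misreading reading 2 could do (illustration only).**
- Growing effect, 0.02, 0.04, 0.06: ΔQALY = 0.005 + 0.015 + 0.015 = 0.035. The allocation coefficient is 0.02, which is 0.015/0.035 = 43% too low, or 0.015 × £20,000 = £300 of net benefit.
- Constant effect, 0.02 throughout: ΔQALY = 0.875 × 0.02 = 0.0175. The allocation coefficient is 0.02/0.0175 = 1.14 times the increment, about 14% too high.
- Period cost differences of +£100, −£50 and −£200: ΔCost = −£150, while the allocation coefficient is +£100. With the growing utility effect, the ratio is −150/0.035 ≈ −£4,286 per QALY from the correct increments (cheaper and more effective) and 100/0.02 = £5,000 from the raw coefficients.

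**The case against.** The best defence is that repeated rows are evidently intended. The predictor list speaks of observations over time within participants, and 8.4 repeatedly calls this a linear mixed model. The sentence about totals can mean that totals are derived from the model rather than entered as its outcome. Equation 1 and the visit schedule already fix the QALY weights, so a competent analyst could work out the contrast. This stands against any claim that the model cannot be fitted at all or cannot yield the increments. It does not supply the missing statement of what the rows are, how time enters and which combination feeds the ICER.

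A reader might infer that the SAP takes the allocation coefficient as the 12-month increment and so understates benefit by a known amount. The document does not support this. It defines the ICER as a difference in costs over a difference in QALYs and never equates either with a coefficient.

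A reader might also infer that *pattern mixed* makes the base case a missing-not-at-random model. Sections 8.4 and 8.5 confine pattern-mixture modelling to sensitivity analysis, so this is mostly a wording slip.

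Section 8.3 separately plans bootstrapped mean differences in costs and QALYs without tying them to this model, so not every economic result depends on it. The economic evaluation is also a secondary, pilot aim of a feasibility trial, and no decision rule rests on the ICER.

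**Conclusion.** The defect is real. As written, the outcome level and the model terms contradict each other, and the literal model is not identified (rank 3 of 5, random effect inseparable from the residual). The visit-level reading is estimable but lacks the contrast that turns it into an incremental cost and QALY. This goes beyond missing detail, because one of the two descriptions has to change.

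It should be fixed, but it does not threaten the trial's primary feasibility outcome. No bias can be quantified from the document. The 43%, £300, 14% and ICER figures above rest on assumed effect profiles and on an assumed analyst error. They show only that the size, and even the sign, of an error could vary.

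Leaving out the minimisation factors is a secondary point: they are needed for randomisation and therefore available for adjustment. Whether baseline cost is collected cannot be told from the SAP, so its absence from the cost model is not shown to be an error.

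**What to change.** Choose one model, name it and use that name throughout.

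- **Option A, totals.** One row per participant. Regress total QALY and total cost each on allocation, baseline utility, carer age, relationship and gender, with no time, interaction or random terms. The allocation coefficients are the increments. Bootstrap costs and QALYs jointly by participant within arm.
- **Option B, visits.** A linear mixed model on utility at 3, 6 and 12 months and on cost per period, with categorical time, allocation by time and the same covariates. State that incremental QALY = 0.25·d(3m) + 0.375·d(6m) + 0.25·d(12m) and that incremental cost = the sum of the period differences.

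Under either option, add baseline cost to the cost model only if it is collected. Replace *pattern mixed* in 8.3 with the chosen model's name, and keep pattern-mixture for the MNAR sensitivity analysis. Align 8.4 with the choice, including the level at which costs and QALYs are imputed.

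The cost is a few lines of SAP text and no new data. The SAP, dated 10/11/2025, says that it preceded the end of data collection and database lock. The current lock status cannot be told from the document. If the data have since been analysed, the change should be dated and reported as a later clarification.

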5.2 Secondary Outcomes

Secondary outcomes include validated outcome measures, NHS and social care resource use and other cost data (health economics), participant demographics such as age, relationship to person with Parkinson's, gender.

Validated outcomes measures can be grouped into carer burden, mental health, process, and quality of life measures. Caregiver burden will be measured using the short form 12-item Zarit Burden interview (ZBI-12). Item responses range from 0 (never) to 4 (almost always), and higher scores indicate greater distress.

Mental health measures consisted of scales to capture depression and anxiety. Depression will be measured using the Center for Epidemiologic Studies Short Depression Scale (CES-D-10). The CES-D-10 consists of 10 questions each with 4 responses from 'rarely or none of the time (less than 1 day)' to 'all of the time (5-7days)'. Anxiety will be measured using the generalised anxiety disorder scale (GAD-7 scale) which consist of asking caregivers to respond to seven questions around different areas of anxiety they have felt over the previous two weeks, each with four possible responses from 'Not at all" to "Nearly every day".

Process measurements include resilience, quality of relationship, self-efficacy, and carer burden. Resilience will be measured using the Resilience Scale (RS-14) which consist of 14 questions grouped into areas of self-reliance, purpose, equanimity, perseverance, and authenticity. Each question has a response between 1 (strongly disagree) to 7 (strongly agree). Quality of relationship will be measured using the Dyadic Relationship scale. This consist of 11 questions measuring the impact of the provision and receipt of family care. There are four levels of response to each question. Strongly Agree (0) to Strongly Disagree (3). Self-efficacy will be measured using the General Self-Efficacy scale(1) which consists of 10 questions with 4 responses to each question from 'not at all true' to 'Exactly True'. The positive aspects of caregiving scale (PACS) ((2)) consists of nine items related to positive aspects of caregiving each with a five response scored Likert scale from 'disagree a lot (1)' to 'agree a lot (5)'. An overall PAC score can be calculated (ranging from 9 to 45) with a higher score reflecting a more positive perception of the caregiving experience.

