5.3 Follow-up

Online questionnaires will be used as the primary mode of data collection. Participants will be sent a personalised link to self-complete questionnaires online using Qualtrics. Data will be collected at baseline (T0),), 3 months after baseline (T1), 6 months after baseline (T2), and 12 months after baseline (T3). Baseline measure will be collected prior to randomisation and will include demographic data such as age, gender, ethnicity, marital status, sexual orientation, socioeconomic status, education level, carer relationship, usual carer support, length of caring. Where data collection surveys are not completed a reminder will be sent via email to prompt participants to complete. After this, researchers will contact participants and collect data through interview via telephone or internet-based service. Although effort will be made to obtain follow-up data as close as possible to the relevant timepoints, it is anticipated that there may be some variation. T1, T2, and T3 follow-up will be acceptable up to 2 weeks early and 4 weeks late. Data will be stored on a secure password protected, purposely designed electronic database. Each participant will be randomly assigned a trial identify code at the point of their randomisation for use on CRF forms, electronic database, and other trial documentation. CRF data and electronic forms will be treated as confidential documents and held securely in accordance with regulations. The researcher will make an independent, separate, and confidential, record of participant name, age, date of birth, and trial number to permit identification of all trial participants as needed.

[figure not shown]

Figure 1: Planned flow of participants through trial

6: Data

6.1Data monitoring

Trial processed and data will be monitored throughout the trial with updated provided monthly at the trial management group meetings. Data collected during the course of the trial will be checked during the trial to offer quality assurance. As this is a feasibility trial, quality assurance will also allow the team to assess issues such as incomplete data collection forms, which may suggest misunderstanding, unwillingness to complete certain questions, or misunderstanding of data collection forms. This will contribute to the findings of the feasibility study and allow flexibility and changes to trial processes during the trial (with changes to the protocol noted and ethical approval for adjustments sought where necessary.

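### The cost model adjusts for baseline utility but not baseline cost, so incremental cost is estimated less precisely than it could be, provided resource use was recorded at T0

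*SAP*

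**What the plan says.** SAP section 8.3 models both economic outcomes in the same way: "Total costs and total QALYs for each patient will be estimated using a pattern mixed linear regression model". One list then serves both: "Each model will include the following predictors". It contains allocation, time, "Allocation x time interaction term", "Baseline utility score" and a within-participant covariance structure. No baseline cost or prior resource use appears in it.

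The costed service use in section 8.2.1 is "Costs of resource use at follow-up". On what is measured and when, section 5.2 says "Secondary outcomes include validated outcome measures, NHS and social care resource use and other cost data (health economics", and section 5.3 says "Data will be collected at baseline (T0", followed by "3 months after baseline (T1), 6 months after baseline (T2), and 12 months after baseline (T3". No section says outright that resource use is asked about at T0. Section 4 minimises on carer age, gender and relationship to the person with Parkinson's.

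**The concern.** Baseline utility is the baseline value of the QALY outcome, so it suits the QALY model. In the cost model it is only an indirect stand-in for earlier service use. If people who used more services before randomisation go on to use more afterwards, leaving baseline cost out leaves explainable variation in the residual. A chance difference between arms in prior use is then largely uncorrected.

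The cost difference feeds the ICER, the NMB and the CEACs. The economic component exists to refine methods for a definitive trial, so the covariate list is itself something likely to be carried forward.

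**Working it through.** **Does anything else in the SAP supply the adjustment?**
- Minimisation (section 4) does not include prior service use.
- Multiple imputation (section 8.4) may draw on other observed variables, but it deals with missing values and does not adjust the between-arm cost difference.
- Baseline cost might enter as a T0 response through the time terms. The SAP does not say so, and section 8.2.1 costs follow-up use only.

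So, as written, the cost model has no baseline cost term.

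**How much would it matter?** The SAP gives no figure to reproduce: no sample size, cost SD or cost correlation. The following are assumptions: 20, 30 or 50 per arm; correlation ρ between baseline and follow-up cost of 0.1 to 0.7; correlation r = −0.2 between utility and cost at either time; one follow-up cost per person, standardised and normal; no true cost difference.

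1. Typical (1 SD) chance imbalance in baseline cost, in SD units: √(2/n) = 0.316, 0.258 and 0.200 for n = 20, 30 and 50 per arm.

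2. SE ratio of a baseline-cost-adjusted to a wholly unadjusted estimate: √(1 − ρ²).

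3. The relevant comparator is the planned, utility-adjusted model. The partial correlation is ρₚ = (ρ − r²)/(1 − r²) = (ρ − 0.04)/0.96, and the SE ratio is √(1 − ρₚ²). For ρ = 0.5: ρₚ = 0.46/0.96 = 0.479, and √(1 − 0.2296) = 0.878.

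4. Share of a baseline-cost imbalance reaching incremental cost under utility adjustment only: ρ − r² = ρ − 0.04.

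5. Simulation of both models (4,000 replicates per setting), which also picks up the cost of estimating one more coefficient:

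| ρ (assumed) | SE ratio vs no adjustment | SE ratio vs planned model, formula | SE ratio vs planned model, simulated | Share passed through, formula | Share passed through, simulated |
|---|---|---|---|---|---|
| 0.1 | 0.995 | 0.998 | 1.00-1.01 | 0.06 | 0.04-0.08 |
| 0.3 | 0.954 | 0.963 | 0.96-0.98 | 0.26 | 0.24-0.27 |
| 0.5 | 0.866 | 0.878 | 0.89 | 0.46 | 0.45-0.47 |
| 0.7 | 0.714 | 0.726 | 0.73 | 0.66 | 0.65-0.67 |

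The simulated ranges run over the three sample sizes. With baseline cost added, the share passed through is about 0 (−0.02 to 0.02). The mean estimate is near 0 under both models, so there is no systematic bias.

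6. Scale of a typical imbalance: at 30 per arm and ρ = 0.5, 0.258 × 0.46 = 0.12 SD. The SE of the utility-adjusted estimate is 0.26 SD, so the shift is 0.12/0.26, or about 0.46 of a standard error.

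**The case against.** The strongest reply is that nothing here is invalid. A randomised cost comparison adjusted for baseline utility is a legitimate estimate, the bootstrapped interval already reflects chance variation in prior service use, and this is a pilot economic analysis. That stands, and it limits the point to efficiency.

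Four stronger readings are tempting, and the document does not support them.
- *Incremental cost is biased.* Randomisation prevents this on average.
- *Chance imbalance and lost precision are two separate harms.* They are one effect seen conditionally and unconditionally; the typical shift is a fraction of the standard error.
- *Baseline resource use is certainly in the dataset.* Sections 5.2 and 5.3 together make it a reasonable inference, but the same sentence in 5.2 also lists demographics, which 5.3 places at baseline, so 5.2 is not a list of items measured at every visit. The examples of baseline content in 5.3 do not name service use, although that list is open-ended.
- *The variance falls by 16% to 49%.* That is 1 − (1 − ρ²) = ρ² for ρ from 0.4 to 0.7. It compares with no adjustment at all and leaves out low correlations.

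The model's time levels are also not fully spelled out, so a T0 cost response cannot be excluded absolutely. Section 8.2.1 makes it the less natural reading.

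**Conclusion.** The point holds as one of efficiency. The shared predictor list gives the QALY model the baseline value of its outcome and gives the cost model none. Against the planned model, adding baseline cost lowers the standard error of incremental cost by nothing at an assumed correlation of 0.1, and by about 2-4% at 0.3, 11% at 0.5 and 27% at 0.7. These figures rest on correlations and sample sizes that the SAP does not give, and on normal costs at a single follow-up. Real costs are likely to be skewed and could give a different correlation.

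The effect is confined to the exploratory ICER, NMB and CEACs and to the method handed to the definitive trial. The primary feasibility outcome is untouched. The improvement is worth making because it costs little and, by the SAP's own account, the plan was written before the database was locked.

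**What to change.** First check whether the baseline questionnaire asks about resource use, and state the answer in sections 5.3 and 8.2.1.

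For the categories recorded at T0, split the predictor list in section 8.3 by outcome. The cost model gains baseline cost: T0 use multiplied by the same unit costs, for the perspective being analysed. The QALY model keeps baseline utility. Add baseline cost to the imputation model in section 8.4 as well. State that the time levels in the cost model are follow-up visits only, so that baseline cost is not also treated as a response.

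The cost is some SAP wording, costing one more time point with unit costs already needed for follow-up, and one extra model parameter, which at a very low correlation buys no precision. No new data are needed where T0 use was recorded. If it was not recorded, the planned model stands, because recruitment had ended when the SAP was written; report the gap and have the definitive trial collect resource use at baseline.
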